# Randomisation

The proportion of eligible participants willing to be randomised will be collected through the use of screening logs (Lancaster *et al.*, 2004). Participants will be randomly allocated to a control group or experimental group following the collection of baseline data. Block randomisation at a ratio of 1:1 will be used to ensure both groups comprise the same number of participants (Suresh, 2011). Patients will be randomly allocated according to the days of the week they attend the unit for haemodialysis, as opposed to at an individual level. As the renal unit is an open environment allocation according to shift pattern will reduce the risk of participants within the control group viewing implementation of the intervention, which would introduce potential contamination (Mc Daid *et al.*, 2006). Sealed envelopes will contain the allocation and these will be stored in a locked filing cabinet on site, and will be opened once consent and baseline data have been obtained. Participants who are randomly allocated to the control group will be instructed not to participate in any art activities during

their haemodialysis sessions throughout the study, but that once data collection is completed they will be provided with art supplies and participate in a facilitated session.

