#### Data analysis

Data analysis will be conducted using the Statistical Package for the Social Sciences (SPSS v 24). Descriptive statistics will be used to present baseline demographic and clinical data Categorical data will be presented as frequencies and percentages, while continuous data will be presented as means and standard deviations. Recruitment, participation and retention rates will be reported and presented in a CONSORT flow diagram (Eldridge *et al.*, 2016). The proportion of patients who were eligible for recruitment, who consented to participation and who completed the study will be calculated and presented with 95% confidence intervals. Exploratory inferential statistics will be conducted, but no conclusions on the effectiveness of the intervention will be made from the results. Independent t-tests (or the non-parametric equivalent Mann-Whitney U) will be conducted to compare the scores of the experimental group and control group. The majority of arts-based intervention research involves pre-and-

post-test designs; therefore a repeated measures t-test (or the non-parametric equivalent Wilcoxon Matched Pairs test) will also be conducted to compare the mean scores of the experimental before and after receiving the intervention. An analysis of variance will be conducted to explore any potential sub-group analysis that may be relevant within a future RCT.

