4.1 Sample size for feasibility RCT and economic evaluation

A sample size of 30 is recommended by the NIHR's Research Design Service for the estimation of a parameter, such as sample size, recruitment or attrition rate, for a definitive randomised controlled trial, although they recognise that advice varies from 24 to 50 participants. Due to the increased risk of identifying a statistically significant result with larger sample sizes, and practical limitations of a small, single centre study, a sample size of 30 was selected for the feasibility RCT. A university statistician was consulted who confirmed that a sample of 30 was an appropriate sample size to meet the objectives of the study. A more comprehensive overview of the sample size decision is available in the study protocol.

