Secondary quantitative outcomes: Chi squared tests will be conducted to establish whether the experimental and control group differ significantly in baseline demographic and clinical data. Completion of the KDQOL-SF36, HADS and EQ-5D-5L will be presented as proportions and rates. A cost consequence analysis will be used to provide a comparative overview of differences in costs and outcomes of participants in the experimental and control group.

Qualitative outcomes: The semi-structured interviews and focus groups will be recorded and transcribed verbatim. Inductive thematic analysis will be used to analyse the data collected. Investigator triangulation, method triangulation and data source triangulation will be used to ensure validity of the identified themes. A more comprehensive description of qualitative analysis is available in the study protocol.

Clinical outcomes: Exploratory inferential statistics will be conducted, but no conclusions on the effectiveness of the intervention will be made from the results. Independent t-tests (or the non-parametric equivalent Mann-Whitney U) will be conducted to compare the scores of the experimental group and control group. The majority of arts-based intervention research involves pre-and-post-test designs; therefore a repeated measures t-test (or the non-parametric equivalent Wilcoxon Matched Pairs test) will also be conducted to compare the mean scores of the experimental before and after receiving the intervention. An analysis of variance will be conducted to explore any potential sub-group analysis that may be relevant within a future RCT. The amount of time taken to conduct this analysis will be reported to inform feasibility.

6 Analysis details

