6.2 Patient Baseline Characteristics

The median (interquartile range) will also be presented for skewed data

- Age, mean (SD)
- Gender, no.(%)
- Education, no.(%)
- Dialysis vintage, mean (SD)
- Ethnicity, no.(%)
- Clinical Frailty Scale, no.(%)
- Number of co-morbidities, mean (SD)
- KDQOL-SF36
- EQ-5D-5L
- HADS
- Patient Resource Use Log

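### The SAP plans chi-squared tests of baseline differences between arms: the test does not fit age, dialysis vintage or co-morbidity count, is unreliable for sparse categories, and cannot show balance in 30 patients

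*SAP*

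**What the plan says.** SAP section 5, under the secondary quantitative outcomes: "Chi squared tests will be conducted to establish whether the experimental and control group differ significantly in baseline demographic and clinical data". No significance level is given, the test is not confined to categorical variables, and there is no provision for exact tests or for merging categories.

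SAP 6.2 lists the baseline characteristics. Age, dialysis vintage and number of co-morbidities are to be given as mean (SD), with median (IQR) added for skewed data. Gender, education, ethnicity and the Clinical Frailty Scale are to be given as number and percentage. KDQOL-SF36, EQ-5D-5L, HADS and the resource use log are also listed. SAP Table 1 describes the frailty scale as having nine points.

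SAP section 5 opens by planning descriptive statistics for the same baseline data. The protocol (Phase 2, Data analysis) has only that part: "Descriptive statistics will be used to present baseline demographic and clinical data". It plans no baseline significance test.

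On size, SAP 4.1 says that "a sample size of 30 was selected for the feasibility RCT". The protocol (Randomisation) says "Block randomisation at a ratio of 1:1 will be used to ensure both groups comprise the same number of participants", and then: "Patients will be randomly allocated according to the days of the week they attend the unit for haemodialysis, as opposed to at an individual level".

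**The concern.** There are three separate problems.

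- **Wrong test for some items.** Chi-squared compares category counts. Three of the seven demographic and clinical items in SAP 6.2 are measurements or counts, and no cut-points are given for them.
- **Sparse cells.** With 30 patients, an item with several levels has expected counts at which the chi-squared approximation is not dependable.
- **Wrong purpose.** The stated aim is to establish whether the arms differ. At this size a non-significant result is compatible with a large imbalance, and a significant one among several tests may be chance. This problem remains even if the sentence was meant for categorical items only.

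At stake is how the baseline table is read: p-values without a sound basis, false reassurance about imbalance, or a chance flag. The test also sits awkwardly with the protocol's own criticism, in its sample size discussion, of inappropriate hypothesis testing in feasibility studies.

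**Working it through.** **Inputs.** Total 30 (SAP 4.1). Allocation 1:1 (protocol, Randomisation), so 30/2 = 15 per arm; this is derived, not stated. Alpha 0.05 two-sided and independent patients are assumptions. The sample of 30 is a rule of thumb, so there is no power figure in the plan to reproduce.

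**1. Chi-squared on a measurement.** Suppose all 30 values are distinct, as is plausible for dialysis vintage. The table is 2 × 30 with one patient in each column and expected count 0.5 in each cell.
- Contribution per column: (1 − 0.5)²/0.5 + (0 − 0.5)²/0.5 = 1
- Total: chi-squared = 30 on (2 − 1)(30 − 1) = 29 df, p = 0.41

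This result is the same however the patients are divided 15 and 15, even if every value in one arm exceeds every value in the other. The test carries no information unless the values are grouped, and no grouping is planned. Co-morbidity counts will have ties, but chi-squared would ignore their order and the cells would be sparse.

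**2. Sparse categories.** The mean expected count per cell is 15/k for k levels.

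| Levels k | 15/k |
|---|---|
| 2 | 7.5 |
| 3 | 5.0 |
| 4 | 3.75 |
| 5 | 3.0 |
| 9 (full frailty scale) | 1.67 |

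Any category holding fewer than 10 of the 30 patients has an expected count below 5 in each arm. Exact enumeration of the 2 × 2 test at 15 per arm, with the same true prevalence in both arms, gives an actual type I error of 2.5% at 10% prevalence and 0.5% at 5% prevalence, against a nominal 5%.

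**3. What a non-significant result can hide.** Take 5/15 v 10/15, a gap of 33 points.
- Pooled proportion 0.5; SE under the null √(0.5 × 0.5 × 2/15) = 0.1826
- z = 0.3333/0.1826 = 1.826; chi-squared = 3.33; p = 0.068
- Unpooled SE √(2 × (1/3)(2/3)/15) = 0.172; 95% CI for the gap 0.333 ± 1.96 × 0.172, about −0.4 to 67 points

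Power by normal approximation is Φ[(difference − 1.96 × null SE)/alternative SE].
- True 33% v 67%: Φ[(0.333 − 0.358)/0.172] = Φ(−0.14) = 44% (exact enumeration 44%)
- True 40% v 60%: Φ[(0.200 − 0.358)/0.179] = Φ(−0.88) = 19% (exact 18%)
- About 80% is reached only at 25% v 75%

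There is a limit on the other side. Starting from 5/15, the first significant contrast is 11/15, a 40-point gap with p = 0.028. Near zero a smaller gap suffices: 0/15 v 4/15 gives p = 0.032.

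**4. False positives.** SAP 6.2 has seven demographic and clinical items. With seven independent tests at 5%, the chance of at least one false difference is 1 − 0.95⁷ = 30%. With only the four items to which chi-squared applies it is 1 − 0.95⁴ = 19%. Sparse tables run below their nominal level (step 2), so 30% is an upper figure.

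**The case against.** The best defence is that this is loose drafting with little consequence. SAP section 5 distinguishes categorical from continuous data shortly before the sentence, so the authors may have meant categorical items only. Descriptive summaries are planned in both documents, so readers would see the figures beside any p-value. Both points are fair. They reduce the harm, but the text still sets no such limit, and the third problem remains for the categorical items.

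A reader might go further than the documents allow in four ways.

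- **That chi-squared is planned for HADS, KDQOL and EQ-5D-5L.** This is not established. The protocol's list of baseline demographic and clinical data (Feasibility measures) omits them and treats HADS and KDQOL as clinical outcome measures. SAP section 5 gives scores their own test, the t-test or Mann-Whitney. SAP 6.2 does list the questionnaires among baseline characteristics, so the scope is ambiguous and no more.
- **That the false-positive risk is 43%.** That is 1 − 0.95¹¹, which counts the three questionnaires and the resource use log as well. It falls with the scope just described.
- **That the tests would mislead a decision.** Neither document says that non-significance will be taken as balance, or that these p-values will choose covariates for the definitive trial. The primary outcomes are recruitment and retention, acceptability, and log completion; progression depends on recruitment and acceptability.
- **That every large imbalance would be missed.** Step 3 shows that gaps of 40 points or more can reach significance.

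It could also be said that allocation by dialysis days makes baseline comparison more useful. Seeing the size of any imbalance is indeed useful. The ordinary chi-squared test, however, assumes independent patients, so this allocation weakens its p-values further.

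**Conclusion.** The concern holds within limits. As written, the SAP applies chi-squared without restriction. It does not fit age, dialysis vintage or number of co-morbidities, it is unreliable for sparse items such as the frailty scale, and it is given a purpose that about 15 patients per arm cannot serve. The p-value and power figures in step 3 rest on 15 independent patients per arm and two-sided alpha 0.05. Allocation by dialysis days assures neither equal arms nor independence. The consequence is confined to the baseline table. It is worth correcting because the SAP adds a test that the protocol does not have and the correction is simple.

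**What to change.** Delete the chi-squared sentence from SAP section 5. Keep the descriptive summaries already set out there and in SAP 6.2, which agree with the protocol. State that they will be shown by allocated arm, which the SAP does not now say, and without p-values. Judge any imbalance by its size and likely prognostic importance.

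Replacing chi-squared with t-tests for the continuous items would mend the first problem but not the third: at 15 per arm an observed difference of about 2.048 × √(2/15) = 0.75 SD is needed for p < 0.05.

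Standardised differences may be added but are optional. Their standard error is about √(2/15) = 0.37, so they should be read as descriptive only.

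The cost is one sentence removed and a short phrase added. No data collection changes, and there is slightly less analysis to do.

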6.1 Recruitment and follow-up patterns

Recruitment and follow-up patterns will be presented in a CONSORT flow diagram and an overview of eligibility, reasons for non-recruitment, and reasons for withdrawal will be recorded and included in the flow diagram.

6.2 Patient Baseline Characteristics

The median (interquartile range) will also be presented for skewed data

- Age, mean (SD)
- Gender, no.(%)
- Education, no.(%)
- Dialysis vintage, mean (SD)
- Ethnicity, no.(%)
- Clinical Frailty Scale, no.(%)
- Number of co-morbidities, mean (SD)
- KDQOL-SF36
- EQ-5D-5L
- HADS
- Patient Resource Use Log

6.3 Clinical Outcome Measures

- Week 3, 6, and 12: KDQOL-SF36
- Week 3, 6, and 12: EQ-5D-5L
- Week 3, 6 and 12: HADS

6.4 Patient Resource Use Log (Administered at baseline, week 3, 6 and 12)

- Home care worker (nhs), no.(%) and mean (95%CI)
- Home care worker (paid), no.(%) and mean (95%CI)
- Meals on wheels (nhs), no.(%) and mean (95%CI)
- Meals on wheels (paid), no.(%) and mean (95%CI)
- Other care visits, no.(%) and mean (95%CI)
- GP visits at surgery, no.(%) and mean (95%CI)

- -Duration of visit, mean (95%CI)
- GP telephone consultations, no.(%) and mean (95%CI)
- GP Home visit, no.(%) and mean (95%CI)
- Calls to out-of-hours, no.(%) and mean (95%CI)
- Visits to out-of-hours, no.(%) and mean (95%CI)
- Nurse visits at surgery, no.(%) and mean (95%CI)
- Nurse telephone consultation, no.(%) and mean (95%CI)
- Community/district nurse home visit, no.(%) and mean (95%CI)
- Social worker visits, no.(%) and mean (95%CI)
- Occupational therapist visits, no.(%) and mean (95%CI)
- Other visits, no.(%) and mean (95%CI)
- Visits to A&E, no.(%) and mean (95%CI)
- Visits to hospital clinic (kidney related), no.(%) and mean (95%CI)
- -Duration of visit, mean (95%CI)
- Visits to hospital clinic (not kidney related), no.(%) and mean (95%CI)
- -Duration of visit, mean (95%CI), mean (95%CI)
- Admissions to hospital/ residential unit, no.(%) and mean (95%CI)
- -Duration of stay (days), mean (95%CI)

7 Additional information

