# Data analysis

A cost-consequence analysis is recommended by the National Institute of Health Research for both complex interventions and feasibility studies where the outcomes of interest are not clear (Hunter and Shearer, 2014). Costs and outcome measure data for both the intervention and control group will be presented using means and 95% confidence intervals in order to show a general overview of the economic costs of the intervention, and differences in resource use and outcome measures between groups. Completion rates and missing data for the Patient Service Use Log and the EQ-5D-5L will be presented as frequencies to assess the feasibility of data collection.

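### SAP 6.4 puts a 95% CI on the mean of every service item at about 15 per arm: it collapses to 0 to 0 when nobody used the service, and the ordinary t interval goes below zero with one to three single-contact users

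*SAP*

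**What the plan says.** SAP 6.4 lists 20 service items, each with a number (%) and a mean with 95% CI, for example "Admissions to hospital/ residential unit, no.(%) and mean (95%CI". Four duration lines have the mean and interval only, for example "Duration of stay (days), mean (95%CI". The log is completed at baseline and at weeks 3, 6 and 12.

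Section 6.4 does not say whether the summaries are by arm. The protocol's Phase 4 data analysis section points that way: "Costs and outcome measure data for both the intervention and control group will be presented using means and 95% confidence intervals". SAP section 5 also plans a comparison of costs and outcomes between the two groups.

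On size, SAP 4.1 states that "a sample size of 30 was selected for the feasibility RCT", and the protocol's Randomisation section adds "Block randomisation at a ratio of 1:1 will be used to ensure both groups comprise the same number of participants".

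The one provision for skewness is in SAP 6.2 on baseline characteristics: "The median (interquartile range) will also be presented for skewed data". That section's list includes the log at baseline. Section 6.4 carries no such rule for follow-up, and nothing says what is reported for a service that nobody used. No interval method is named in either document. The software is SPSS v24.

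**The concern.** Service counts over a short study contain many zeros, and some listed items (admissions, A&E visits, meals on wheels) may have few or no users in a group of 15. A symmetric interval on the mean then behaves badly in two ways. If nobody used the service, the sample SD is zero and the interval has no width. If very few did, the interval extends below zero, which a count cannot do.

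What is at stake is how the tables are read. The number (%) column has no interval, so the interval on the mean is the only statement of uncertainty for each item. For an unused item it would show none, when 15 patients leave a good deal.

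**Working it through.** **Inputs**
- N = 30 (SAP 4.1) at 1:1 (protocol, Randomisation), so 30/2 = 15 per arm before attrition.
- 20 service items plus 4 durations, at 4 time points (SAP 6.4). By arm that is 24 × 4 × 2 = 192 intervals.
- Interval method: not stated. The t interval is assumed, and the percentile bootstrap was checked as the alternative.
- Use rates: not stated. Means of 0.02 to 2 contacts per patient per reporting window are assumed. The recall window is not stated either.

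The sample size of 30 is a rule of thumb, and the plan states no interval width or rate, so it has no figure of its own to reproduce here.

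**Fixed examples.** If k of n patients have one contact each, the mean is k/n, SD² = (k − k²/n)/(n − 1), and the interval is mean ± t × SD/√n. At n = 15, t = 2.145. For k = 2: SD = √[(2 − 4/15)/14] = 0.352, and 0.133 ± 2.145 × 0.352/√15 = -0.062 to 0.328.

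| Users of 15 | t interval for the mean | Exact (Clopper-Pearson) 95% CI for % using |
|---|---|---|
| 0 | 0 to 0 | 0 to 21.8% |
| 1 | -0.076 to 0.210 | 0.2 to 31.9% |
| 2 | -0.062 to 0.328 | 1.7 to 40.5% |
| 3 | -0.029 to 0.429 | 4.3 to 48.1% |
| 4 | 0.013 to 0.520 | 7.8 to 55.1% |

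The lower limit is negative when k < t²n/(n − 1 + t²) = 4.601 × 15/18.601 = 3.71, so for k = 1, 2 or 3.

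For no users, the exact upper limit is 1 − 0.025^(1/15) = 0.218. The Wilson upper limit is 3.84/(15 + 3.84) = 0.204. A percentile bootstrap resamples only zeros and also returns 0 to 0.

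**Coverage of the t interval**, n = 15, Poisson counts, 200,000 simulated samples per rate:

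| Assumed mean | No users in sample | Lower limit < 0 | Coverage |
|---|---|---|---|
| 0.02 | 74% | not shown | 26% |
| 0.05 | 47% | not shown | 53% |
| 0.1 | 22% | 74% | 78% |
| 0.2 | 5% | 72% | 95% |
| 0.3 to 2 | not shown | see below | 93-95% |

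The shortfall at low rates is almost exactly the chance of no users, e^(−15 × mean). At 0.05, 1 − e^(−0.75) = 0.528. At 0.1, 1 − e^(−1.5) = 0.777. Given at least one user, coverage is 99.9% and 99.8%. Negative limits remain common up to a mean of about 0.3.

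**Sensitivity**
- Overdispersed counts (negative binomial, k = 0.5 and 0.2): coverage 75% and 70% at a mean of 0.1, then 88-92% and 81-88% at means of 0.2 to 2.
- 12 per arm, Poisson: 45% at 0.05 and 70% at 0.1.
- Both arms pooled, n = 30, Poisson: 45% at 0.02, 78% at 0.05 and 95% at 0.1. With t = 2.045, 4.18 × 30/33.18 = 3.78, so one to three single-contact users still give a negative limit.
- Percentile bootstrap, n = 15, Poisson: no negative limits, but coverage of 53% at 0.05 and 78% at 0.1.

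**The case against.** The strongest reply is that this is descriptive output in a feasibility study and is already partly protected. Each service item carries a number (%), so a reader would see 0 (0%) beside the 0 to 0 interval. SAP 6.2 adds the median (IQR) for skewed data, and its list covers the log at baseline. The Phase 4 primary outcome in SAP 2.1 is completion of the log and missing data. No progression criterion uses these intervals. All of that stands, and it limits the importance of the point.

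It is also fair that the arithmetic rests on assumptions. Negative limits follow from a t interval that the plan does not name, and rarity is assumed. From a Poisson mean of 0.2 upward, coverage is close to nominal. Low coverage and zero width are not two separate faults at the lowest rates: they are nearly the same event, and once anyone has used the service the interval over-covers.

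Two things remain. The collapse to 0 to 0 needs no assumed rate and occurs under both methods whenever an item has no users. And the number (%) that is meant to protect the reader has no interval of its own.

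**Conclusion.** The point holds for rarely used items, as a minor one. For any item with no users, the planned interval shows no uncertainty where the data allow up to 22% of patients to be users. For one to three single-contact users, the ordinary t interval includes impossible values. These results assume about 15 per arm, and the negative limits also assume a t interval. The coverage figures depend further on the assumed rates and on Poisson counts, and are lower with overdispersion.

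Three stronger conclusions might be inferred, and the material does not support them:
- **That all the item-level intervals are unreliable.** Under Poisson use, coverage is 93-95% at means of 0.2 and above.
- **That these intervals will be used to cost the definitive trial.** Neither document says so. The protocol describes the output as a general overview, and its Phase 4 section says that a full cost-effectiveness evaluation is not recommended at this stage.
- **That a bias-corrected bootstrap CI for total cost would be a sound replacement.** At n = 15 with assumed lognormal costs it covered about 84-86% against 85% for the t interval, and 79% against 75% for a more skewed distribution. That is little or no gain.

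A separate limit applies to any patient-level interval here, including those proposed below. The protocol says "Patients will be randomly allocated according to the days of the week they attend the unit for haemodialysis", so such intervals ignore any similarity within dialysis shifts.

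**What to change.** Change the SAP 6.4 table shells, and nothing in data collection or conduct:

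1. State that number (%) means patients who used the service at least once, and give it an exact (Clopper-Pearson) or Wilson 95% CI with the method named. An item with no users in 15 then reads 0 (0%), 0 to 21.8% by the exact method.
2. Replace the 95% CI on item-level means with mean (SD) and median (IQR), extending the skewed-data rule of 6.2 to weeks 3, 6 and 12.
3. Report the four durations among users only, descriptively and with the number of users shown. With no user or one user, no interval can be computed there in any case.
4. State whether the tables are by arm. The protocol's Phase 4 analysis sentence speaks of costs and outcome data but goes on to mention resource use, so one SAP line should say that item-level use is summarised as above.

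The cost is that item-level means lose their interval and the tables grow somewhat. The exact interval is also conservative: its coverage was 98.0-99.7% for true proportions of 2-30% at n = 15.
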